## 1.0 STUDY SCHEMA

Patients with obstructive sleep apnea hypopnea syndrome (OSAHS) who are candidates for base of tongue (BOT) resection.

Informed consent obtained

Patient enrolled into study

Surgery

Patient Follow-up  
1. Post Op pain diary  
2. First post-operative visit.  
3. Routine 3-month follow-up.

## 2.0 SUMMARY

This is a prospective observational study that will collect outcome data for patients who choose to undergo transoral robotic assisted tongue base operations for Obstructive Sleep Apnea Hypopnea Syndrome (OSAHS). The da Vinci® Robotic Surgical System (Intuitive Surgical) is the system used at the University of Alabama at Birmingham (UAB) and will be utilized for this study.

## 3.0 BACKGROUND AND RATIONALE

Obstructive sleep apnea hypopnea syndrome (OSAHS) is a major public health problem, and studies suggest that the incidence of OSAHS may be even higher than estimated.

Transoral base of tongue resections are commonly preformed to improve symptoms in OSAHS, but among surgeons there is not yet consensus as to the best tongue base operation. The difficulty in treating the tongue base is illustrated by the abundance of available procedures – including genioglossus advancement, hyoid advancement, tongue base suspension, radiofrequency treatment, transoral midline glossectomy, submucosal coblation-assisted tongue base resection and recently; transoral robotic-assisted surgery (TORS) for base of tongue (BOT) resection. We will evaluate TORS BOT resection for use in OSAHS by assessing pre- and post-operative OSAHS scores and comparing them to historical data for alternative BOT operations.

Though routine, BOT resection may result in significant post-operative pain leading to dysphagia. In certain patients, major complications such as aspiration pneumonia, malnutrition and dehydration can occur as a result. Thus, reducing post-operative dysphagia is critical to improving patient outcomes and limiting complication-associated hospital admissions. Several studies have addressed the management of post-operative dysphagia, but none have evaluated TORS BOT resections in OSAHS. Additionally, TORS BOT resections for malignant neoplasms have been previously shown by [name] and [name] to be safe and feasible. An outcome analysis of TORS BOT resections for OSAHS may therefore yield recommendations for reducing patient morbidity and mortality.

To evaluate TORS BOT resection as a treatment for OSAHS; patients will serve as their own controls by undergoing assessment for OSAHS pre- and post-operatively. We will characterize patient morbidities associated with surgical correction of OSAHS by reviewing data collected during regularly scheduled follow-up visits (Appendix A), and by patient pain diaries (Appendix B). In addition, we will independently assess dysphagia using the M.D. Anderson Dysphagia Inventory (Appendix C). Our goal is to improve quality of life for future OSAHS patients undergoing BOT resection.

While previous publications have documented the use of robotic assisted oropharyngeal surgery, the transoral approach is considered off-label use of robotic assisted surgery. Currently the transoral approach is being performed at UAB for oropharynx surgery (HNO 0601). Therefore, we are proposing to perform a series of tongue base resections

in 40 patients to assess this technique at the University of Alabama at Birmingham. The Division of Otolaryngology sees many OSAHS patients a year that would be candidates for operative intervention using the *robotic assisted surgery*. A robotic surgical system is available for this purpose and is currently used by multiple specialties at the University Hospital.

#### **4.0 OBJECTIVES:**

##### **4.1 Primary Objective:**

The primary objective of this study will be to determine if base of tongue (BOT) resection with transoral robotic-assisted surgery (TORS) yields improvements in OSAHS with reduction in apnea/hypopnea index.

#### **5.0 TRIAL DESIGN**

This trial is a single institution non-randomized study to evaluate the efficacy and safety of transoral robotic-assisted surgery (TORS). We propose to use the da Vinci ® Robotic Surgical System which is currently in place at UAB to perform surgical resection in 40 patients with OSAHS.

Patients with OSAHS, who present to the Division of Otolaryngology and are scheduled for base of tongue surgery and enrolled to this study, will be given a pain diary to start the morning of surgery to continue for a total of two weeks following surgery. Patients will also be asked to complete the MD Anderson Dysphagia Index (MDADI) swallowing questionnaire to be done prior to surgery, at their post operative clinic visit and at approximately three months following surgery. A sleep study will be done two to three months following surgery if allowed by participant's insurance carrier. A medical record review will be done on all participants who complete the diary and questionnaire.

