## **8.0 STUDY TREATMENT**

Robotic assisted surgery will be performed in standard fashion. If at any point during the procedure the area for resection is not well visualized, or the resection is compromised, or the procedure is felt to be unsafe (for example potential injury to teeth or gums), the procedure will be aborted. Participants will then be presented an alternative treatment plan for this condition.

Post-operative care and discharge will be performed in the routine manner for OSAHS. Medical records will be reviewed from this period of routine care to determine what effects, good and/or bad, this procedure has on the patient. These records will include hospital and clinic records such as clinic and hospital notes, anesthesia notes, radiological imaging and speech pathology information. Patients will be followed post-operatively using standard practice.

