#### **9.2.2 Adverse event reporting definitions**

In the event of an adverse event the first concern will be for the safety of the subject. Serious adverse events to be reported is

defined as any sign, symptom or medical condition that emerges during surgery through a period of 30 days following surgery that (1) was not present prior to surgery and is not a chronic condition that is in the patient's medical history OR (2) was presented prior to surgery but worsened as a result of surgery, AND that meets any of the following regulatory serious criteria:

- Results in death
- Is life-threatening
- Requires or prolongs inpatient hospitalization
- Is disabling
- Is a congenital anomaly/birth defect
- Is medically significant or requires medical or surgical intervention to prevent one of the outcomes listed above.

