#### **9.2.4 Safety Monitoring**

- [name] will be responsible for review of the data. If at any time it is determined that the risks of participation outweigh the benefits, the study will be reviewed by [name] and the research staff.
- Participant information and adverse events will be evaluated as deemed necessary at the meetings of the Office of Clinical Research for the UAB Division of Otolaryngology – Head and Neck Surgery.
- All events determined to be Serious Adverse Events, whether related to the study procedure or not, will be reported to the Institutional Review Board at UAB.

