### **10.0 SUBJECT EVALUATIONS**

#### **10.1 Baseline evaluations:**

1. Routine medical exam prior to surgery.
2. Dysphagia survey prior to surgery.
3. OSAHS evaluation

**10.2** Pain Diary to be completed by participant daily starting with the day of surgery through 2 weeks post op.

**10.3** Routine follow up exams for three months: (post operative exam and three month follow up exam)

1. Routine medical exam.
2. Assessment for adverse events.
3. Dysphagia survey.
4. OSAHS evaluation (including sleep study if allowed by participant's insurance).

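### Sections 5.0 and 8.0 disagree on whose medical records are reviewed; making review depend on completed post-operative forms could understate morbidity

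*Protocol*

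**What the plan says.** Section 5.0 (Trial Design) presents the study as an evaluation of efficacy and safety in 40 patients. Each patient "will be given a pain diary to start the morning of surgery to continue for a total of two weeks following surgery". The swallowing questionnaire is scheduled three times: before surgery, at the post-operative visit and at about three months. The section ends: "A medical record review will be done on all participants who complete the diary and questionnaire". It does not define what counts as completing either form.

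Section 8.0 (Study Treatment) states the purpose of the review: "Medical records will be reviewed from this period of routine care to determine what effects, good and/or bad, this procedure has on the patient". It lists clinic and hospital notes, anesthesia notes, imaging and speech pathology information, and sets no completion condition. The preceding paragraph says that if the resection cannot proceed well or safely, "the procedure will be aborted".

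Other sections also bear on safety data:

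- Section 3.0 makes morbidity an aim: "We will characterize patient morbidities associated with surgical correction of OSAHS by reviewing data collected during regularly scheduled follow-up visits", together with the pain diaries.
- Section 9.2.2 describes a reportable serious event as "defined as any sign, symptom or medical condition that emerges during surgery through a period of 30 days following surgery" that meets a seriousness criterion.
- Section 9.2.4 adds: "All events determined to be Serious Adverse Events, whether related to the study procedure or not, will be reported" to the institutional review board.
- Section 10.3 lists "Assessment for adverse events" at the post-operative and three-month exams.

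**The concern.** The Section 5.0 sentence selects patients for record review on something observed after surgery. Even on the loosest reading, where the pre-operative questionnaire alone would satisfy the questionnaire part, the diary still has to be kept for two weeks after the operation.

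The protocol itself names courses that could make form-filling harder. Section 3.0 mentions pain leading to dysphagia, with aspiration pneumonia, malnutrition and dehydration as possible consequences. Section 9.1.1 mentions prolonged intubation or re-intubation. If such patients finish the forms less often, their charts are the ones left unread, and record-derived morbidity looks better than it was.

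What is at stake is mainly non-serious morbidity documented in the records (dysphagia care, imaging, speech pathology, anesthesia findings) and events after day 30. The loss occurs at data collection, so an analysis plan cannot recover it.

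**Working it through.** The protocol gives no figure to reproduce here. The check compares the text, then bounds and illustrates the possible effect.

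**1. The two rules side by side**

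| | Section 5.0 | Section 8.0 |
|---|---|---|
| Whose records | Participants who complete diary and questionnaire | No condition stated |
| When status is known | At the earliest, two weeks after surgery | Not applicable |
| Purpose | Not stated | Good and bad effects of the procedure |

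Staff following Section 5.0 would skip charts that Section 8.0, read plainly, says will be reviewed.

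**2. What the other routes cover for a patient with unfinished forms**

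- Serious events to day 30: covered (Sections 9.2.1, 9.2.2 and 9.2.4).
- Adverse events in patients who attend: assessed at both follow-up exams (Section 10.3).
- The chart sources listed in Section 8.0: replaced by neither route.
- Non-serious events, or events after day 30, in a patient who also misses the visits: covered by neither route.

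Taking three months as about 90 days, 90 − 30 = 60 days lie outside the serious-event definition and rest on visits and records.

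**3. Worst-case bound**

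Input: N = 40 (Sections 3.0 and 5.0). Suppose an item is known only from the record review, m patients are unreviewed, and x events are found in the other 40 − m. The true proportion among 40 lies between x/40 and (x + m)/40, a width of m/40.

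| m (assumed) | Width m/40 |
|---|---|
| 1 | 2.5 points |
| 2 | 5 points |
| 4 | 10 points |
| 8 | 20 points |

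**4. Direction of bias**

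Let p be the true morbidity rate, c1 the completion rate among patients with the morbidity and c0 the rate among those without. The expected rate among completers is

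p·c1 / [p·c1 + (1 − p)·c0].

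All three inputs are assumptions. Expected counts are out of 40.

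| p | c0 | c1 | Events / reviewed | Rate seen |
|---|---|---|---|---|
| 20% | 90% | 90% | 7.2 / 36.0 | 20.0% |
| 20% | 90% | 70% | 5.6 / 34.4 | 16.3% |
| 20% | 90% | 50% | 4.0 / 32.8 | 12.2% |
| 20% | 80% | 40% | 3.2 / 28.8 | 11.1% |
| 10% | 90% | 50% | 2.0 / 34.4 | 5.8% |
| 30% | 90% | 50% | 6.0 / 31.2 | 19.2% |

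Equal completion gives no bias. Lower completion among affected patients always biases the rate downward.

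**The case against.** The strongest reply is that this is an ambiguity rather than a contradiction. Section 5.0 does not say that only completers are reviewed, and Section 8.0 does not say that everyone is. One sentence could be naming the patients and the other describing the content. The literal point is correct, but a completion qualifier that limits nothing would serve no purpose. If the sponsor meant everyone, the sentence is misworded and needs the same edit.

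A second reply is that safety is captured elsewhere and the remaining gap is narrow. This stands in part: serious events to day 30 and events assessed at attended visits do not depend on the forms. Section 3.0 also names visit data and diaries as its morbidity sources, and Section 6.2 excludes patients with conditions that would interfere with adherence. That exclusion cannot prevent drop-off caused by the surgery itself, and none of these supplies the Section 8.0 chart sources.

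Third, the abort rule is in a separate paragraph from the record review, so including aborted cases goes beyond reconciling two sentences. That is fair as a reading of the text. But a safety evaluation should count everyone in whom the procedure was started, and aborted cases are part of that experience.

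Finally, the sizes rest on assumed completion rates, and the 60-day figure supposes that the review runs to three months, although Section 8.0 gives no end date. Both limits stand. They concern how large the effect is, not whether the condition exists.

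**Conclusion.** The concern holds. Section 5.0 conditions the record review on post-operative behaviour, Section 8.0 does not, and the protocol leaves the conflict open. Followed as written, Section 5.0 could understate record-derived morbidity, chiefly non-serious events and events after day 30.

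The bias is possible, not established. It requires patients with worse courses to complete the forms less often, and the protocol offers no rates from which to size it. The firm statement is the bound of 2.5 percentage points per unreviewed patient, for items known only from the records and with 40 patients as planned. No section shows that the apnea/hypopnea result depends on this sentence. It should be fixed because the lost information cannot be recovered later and the correction is cheap.

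**What to change.** Replace the last sentence of Section 5.0 with:

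> Medical records will be reviewed for every participant in whom study surgery is started, including aborted procedures, irrespective of diary or questionnaire completion.

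Use that set as the denominator for record-derived morbidity. Section 8.0 then needs no change on this point.

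The cost is one sentence and a few extra chart reviews in patients who, under Section 7.0, have already consented and been registered. The consent form was not available for this review, so confirm that its record access covers participants who do not complete the forms. The reported morbidity figures may look less favourable.

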#### **6.0 PATIENT SELECTION CRITERIA**

##### **6.1 Eligibility Criteria**

1. Any patient with documented OSAHS who is scheduled for tongue base resection at UAB.
2. Age > 19 years
3. Patients must sign informed consent

##### **6.2 Exclusion Criteria**

1. Psychological condition that renders the patient unable to understand the informed consent.
2. Any situation or condition that will interfere with adherence to study activities.

## **7.0 REGISTRATION**

Patients must not start protocol treatment prior to formal registration and informed consent.

### **7.1 Patient Consent**

Patients thought to be candidates for this protocol will be identified by his/her physician. The study will be explained to the patient and a consent form will be given for review.

### **7.2 Patient Screening**

Patients who agree to participate in the study and have signed informed consent will undergo patient screening.

### **7.3 Patient Registration**

Patients, who have signed the informed consent and meet the eligibility criteria, will be entered into the study prior to any protocol therapy. The following information will be required at the time of patient entry:

- Patient's name (or initials) and ID #, hospital chart number
- Verifying Physician's Name
- Eligibility Criteria Information
- Demographic Data (sex, birth, date, race, nine-digit zip code, and method of payment)

## **8.0 STUDY TREATMENT**

Robotic assisted surgery will be performed in standard fashion. If at any point during the procedure the area for resection is not well visualized, or the resection is compromised, or the procedure is felt to be unsafe (for example potential injury to teeth or gums), the procedure will be aborted. Participants will then be presented an alternative treatment plan for this condition.

Post-operative care and discharge will be performed in the routine manner for OSAHS. Medical records will be reviewed from this period of routine care to determine what effects, good and/or bad, this procedure has on the patient. These records will include hospital and clinic records such as clinic and hospital notes, anesthesia notes, radiological imaging and speech pathology information. Patients will be followed post-operatively using standard practice.

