## **9.0 ADVERSE EVENT REPORTING**

### **9.1 Potential treatment hazards**

9.1.1 Injury to perioral structures during the surgical procedure. Use of the robot in transoral surgery has been demonstrated to be safe in a limited data set. However, the use of oral instrumentation for access to base of tongue resections can result in injury to teeth, gums and/or the tongue. The standard risks of surgery include post operative pain and discomfort, bleeding, infection, post operative pneumonia, laryngeal and pharyngeal swelling, difficulty in swallowing, injury to nerves and blood vessels failure to perform resection and adverse reactions or complications from anesthesia. Although very rare, with any surgery there is a risk of life threatening events that may result in persistent or significant disability/incapacity or death. In some cases, a feeding tube may be placed to ensure adequate nutrition and fluid intake. On rare occasions, severe throat edema may require prolonged intubation or re-intubation. There is also a rare risk for instrument breakage and power outage resulting in a shutdown of transoral diagnostic and therapeutic surgical equipment. UAB has backup precautions for these types of situations. It is felt that the use of the robotic assisted surgery will not add additional risks to the standard surgical risks.

9.1.2 Need for additional surgery in cases where TORS cannot be adequately performed.

9.1.4 Confidentiality: As a participant in a UAB protocol that collects data on patients including personal information and disease related information, there is a potential for breach of patient confidentiality.

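### Section 5.0's record-review condition and sleep-study timing do not allow for aborted TORS, so such cases may be missed or an AHI taken after another treatment may enter the TORS result

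*Protocol*

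**What the plan says.** Patients enter the study before surgery: under section 7.3 those who have consented and are eligible "will be entered into the study prior to any protocol therapy". A patient whose operation is stopped is therefore already a participant.

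Section 8.0 gives three grounds for stopping: poor view, compromised resection, or that "the procedure is felt to be unsafe (for example potential injury to teeth or gums), the procedure will be aborted". It continues: "Participants will then be presented an alternative treatment plan for this condition". Section 9.1.2 lists the same event as a hazard: "Need for additional surgery in cases where TORS cannot be adequately performed".

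The primary objective (4.1) is whether base of tongue resection with TORS "yields improvements in OSAHS with reduction in apnea/hypopnea index". The comparison is within patient; section 3.0 says "patients will serve as their own controls by undergoing assessment for OSAHS pre- and post-operatively".

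Two sentences in section 5.0 govern what is collected:

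- Sleep study: "A sleep study will be done two to three months following surgery if allowed by participant's insurance carrier".
- Record review: "A medical record review will be done on all participants who complete the diary and questionnaire".

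The second paragraph of section 8.0 also describes record review, as the way to learn the procedure's good and bad effects, and it provides for post-operative follow-up by standard practice. It limits neither to patients who return the diary and questionnaire.

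**The concern.** An aborted procedure is direct evidence on how well the technique works, and section 5.0 says the trial evaluates efficacy and safety. With 40 patients, a few such cases carry weight.

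The two collection rules in 5.0 leave two openings. First, record review depends on completing a diary that runs for two weeks after surgery and a questionnaire repeated at about three months. A patient who has moved to another treatment plan may not complete them, and the chart would then fall outside the review. Second, the sleep study is tied only to the time since surgery. If an aborted patient has had another treatment by then, a simple before-after difference includes that treatment's effect. Section 3.0 plans to compare TORS with historical data on other tongue base operations. If the later treatment were one of those, the effect of a comparator would be counted on the TORS side.

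Both openings concern data collection. An analysis plan written later cannot recover charts that were never reviewed or treatment dates that were never recorded.

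**Working it through.** **1. The passages side by side**

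| Question about an aborted patient | Section 5.0 | Section 8.0 | Elsewhere |
|---|---|---|---|
| Already enrolled? | Implied | – | Yes (7.3) |
| Record review? | Only if diary and questionnaire are completed | Described without that limit | – |
| Study follow-up continues? | Not addressed for aborts | Standard-practice follow-up for patients generally | Visits in 10.3, aborts not separated |
| Sleep study relative to another treatment? | Two to three months after surgery, insurance permitting; other treatment not mentioned | Alternative plan presented; timing not given | 10.3 repeats the insurance condition |
| Serious adverse events captured? | – | – | Yes (9.2.1, 9.2.2, 9.2.4) |

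Sections 5.0 and 8.0 differ on who has record review. No section relates the AHI measurement to a later treatment.

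**2. Size, for illustration only**

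The one input from the documents is n = 40. Everything else is assumed: k = 2 to 6 aborted (5% to 15%), a mean AHI fall of 15 events/h in completed cases, a 60% response in completed cases, and no change in aborted ones. The calculation also supposes that all 40 have a post-operative sleep study, which the insurance condition does not guarantee.

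*Chance of at least one abort:* 1 − (1 − a)^40.
- a = 5%: 1 − 0.95^40 = 0.871
- a = 15%: 1 − 0.85^40 = 0.998

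*Aborted cases left out rather than counted as no change:* the mean fall is inflated by 40/(40 − k).
- k = 2: 40/38 = 1.053. The mean over all 40 is 15 × 38/40 = 14.25, against 15 in completed cases.
- k = 6: 40/34 = 1.176. The mean over all 40 is 15 × 34/40 = 12.75, against 15.

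*Response:* 60% × (40 − k)/40.
- k = 2: 57%
- k = 6: 51%

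*AHI after another treatment pooled instead:* if the aborted patients' AHI has fallen by d on average, the pooled mean is [15(40 − k) + dk]/40, which is dk/40 above the figure that counts them as no change. With d = 15 this is 0.75 (k = 2) to 2.25 (k = 6) events/h. With d = 0 it is nil, and with negative d it changes sign. The documents give no value for d, so the direction as well as the size is open.

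**3. Precision of the abort proportion**

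Exact (Clopper-Pearson) 95% intervals:
- 2/40 = 5%: 0.6% to 16.9%
- 6/40 = 15%: 5.7% to 29.8%

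Even a small observed count leaves an appreciable abort rate possible, so the interval should accompany the count.

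**The case against.** A reader might infer that the protocol makes aborted patients drop out, or that it credits their later AHI to TORS. It prescribes neither. No section withdraws or excludes them, and none says that an AHI taken after another treatment is pooled. The alternative plan is only presented; a patient may decline it, or may not have had it by the time of the sleep study, and an unchanged AHI would then be measured. Section 4.1 is worded about resection with TORS, so an analyst might well set such a value aside. This stands: both outcomes are possibilities left open by the text.

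A reader might also infer that failures of the technique disappear from the safety record. The documents do not support that. Serious adverse event reporting starts at consent (9.2.1), covers events from surgery to 30 days afterwards (9.2.2) and goes to the institutional review board (9.2.4). Adverse events are assessed at both follow-up visits (10.3). None of this depends on the diary. An abort need not itself be a serious adverse event, but these patients are not outside safety capture.

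The record review in 8.0 has no diary condition and includes anesthesia and hospital notes, where an abort would ordinarily be recorded. That softens the concern, but it also confirms that 5.0 and 8.0 need reconciling.

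Finally, the analysis set, the failure rule and any imputation commonly belong in a statistical analysis plan, which is not shown. Their absence here is no fault, and completed resection is a defensible population for this objective. That stands too. It does not reach the record-review condition or the undated later treatment, which are matters of data collection in the protocol.

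**Conclusion.** The point holds as one about data collection. Section 5.0 conditions record review on completing the diary and questionnaire, contrary to the broader description in 8.0, and times the AHI measurement without regard to whether TORS was completed or another treatment intervened. Followed literally, aborted cases may be missed in record review, or another treatment's effect may enter the TORS before-after change. Either could bias the AHI result.

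The size is unknown. The relative overstatement of 5% to 18% and the drop from 60% to between 57% and 51% rest on an assumed abort rate of 5% to 15%, an assumed response rate, and no change in aborted patients. The bias from pooling cannot be sized or signed from the documents. The change is worth making because the gap cannot be repaired once the data have been collected.

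**What to change.** - **Record review and follow-up.** In 5.0, remove the diary and questionnaire condition, in line with 8.0. State that every enrolled patient in whom robotic surgery is begun has record review and stays in study follow-up.
- **Later treatment.** Record any later OSAHS treatment and its date relative to the sleep study. State that an AHI taken after another treatment does not count as a TORS result.
- **Reporting.** Give the number and proportion of aborted procedures, with an exact 95% confidence interval, beside the AHI result.
- **Left to the analysis plan.** How aborted cases count in the AHI analysis can be set there, for example as non-responders with completed TORS shown separately. Setting the post-operative AHI to baseline is one sensitivity option, not a requirement.

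The cost is a few sentences in 5.0 and 8.0, chart review of a few more patients, and possibly a slightly less favourable efficacy figure.
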